### Patients

We will enroll up to 800 (including 25 – 50 pilot) consenting adults, with American Society of Anesthesiologists (ASA) physical status 1-3, who are scheduled for elective non-cardiac surgery requiring endotracheal intubation with rapid sequence induction for general anesthesia. Written informed consent will be obtained. Participating study centers will be:

- Cleveland Clinic, Main Campus, Cleveland OH
- Tabriz University of Medical Sciences, Tabriz, Iran
- The University of Health Science, Konya City Hospital, Konya, Turkey
- The University of Health Science, Bakırköy [name] Education, and Research Hospital, Istanbul, Turkey

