#### **Secondary outcomes:**

Randomized groups will be compared on the secondary outcome of Intubation failure (yes/no) via chi-square test and the associations reported using relative risk [97.5% confidence interval (CI)]. Randomized groups will be compared on the count of number of intubation attempts using either Wilcoxon-Mann-Whitney test or negative binomial regression, as appropriate. A Bonferroni correction will be applied and a significance criterion of  $0.05/2=0.025$  to control the overall Type I error at 5% level for two secondary hypotheses.

The exploratory and safety outcomes will be reported by study groups without formal statistical testing of the difference.

**Formatted:** Highlight

**Interim analyses** to assess efficacy and futility will be conducted at each 25% of the maximum planned enrollment. We will use a gamma spending function with gamma parameter= -4 for efficacy and -1 for futility.

**Sample size considerations.** **Sample size** is based on the primary outcome of glottis visualization (Cormack and Lehane classification) and the Wilcoxon-Mann-Whitney test. From the literature we assume a distribution of scores for the Direct Laryngoscopy group such that the proportion of patients in categories 1, 2a, 2b, 3 and 4 are 0.50, 0.30, 0.15, 0.04, 0.01, and that for the videolaryngoscopy the proportions are improved to 0.65, 0.25, 0.07, 0.02, 0.01. **We would thus need a total of 384 patients** to detect this difference or larger with 90% power at the 0.05 significance level. Incorporating a maximum of 3 interim analyses and a final analysis with the above-detailed spending functions will require a maximum **of N=438 patients**. Simulations indicate that if the specified difference is a good estimate of the true effect, the expected sample size is about 78% of the maximum sample size, or N=342. **In such a case**, the study will have a very good chance of crossing an efficacy boundary at interim looks 2 or 3.

Formatted: Font color: Red

Formatted: Font color: Red

Formatted: Font color: Light Blue

Because our estimates of laryngeal view are uncertain, **we plan to enroll a maximum of 800 patients in case the treatment effect is somewhat less than anticipated.**

Formatted: Font color: Red

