**Pilot patients:** We will enroll 5-10 pilot patients prior to the start of the study at each study center to familiarize the study team with the protocol and identify any systematic issues that might result in protocol modifications. Pilot patients will be randomized either to McGrath videolaryngoscopy or direct laryngoscopy group in the same manner as it is planned for the study. Pilot patients will not be included in the statistical analysis.

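### The stated expected sample size (78% of 438, N=342) does not follow from the plan's own design inputs, which give about 299 (68%); look sizes, power and expected size for the 800-patient maximum are not stated

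*Combined protocol and SAP*

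**What the plan says.** All of the design figures are in the Interim analyses and Sample size considerations paragraphs of the statistical section.

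- Interim analyses "to assess efficacy and futility will be conducted at each 25% of the maximum planned enrollment", with gamma spending of -4 for efficacy and -1 for futility. Sidedness is not stated, nor whether futility is binding.
- A fixed design needs 384 patients for 90% power at the 0.05 level. "Incorporating a maximum of 3 interim analyses and a final analysis with the above-detailed spending functions will require a maximum" of 438.
- "Simulations indicate that if the specified difference is a good estimate of the true effect", then "the expected sample size is about 78% of the maximum sample size, or N=342". The simulation settings are not given.
- The plan then adds that "we plan to enroll a maximum of 800 patients in case the treatment effect is somewhat less than anticipated". It gives no power, expected size or look sizes for 800.

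The Patients section repeats the cap: "We will enroll up to 800 (including 25 – 50 pilot) consenting adults". The Pilot patients paragraph says "We will enroll 5-10 pilot patients prior to the start of the study at each study center" and "Pilot patients will not be included in the statistical analysis".

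**The concern.** The 342 is the only expected enrolment the plan gives, and it is conditional on the planned effect being true. For a four-look design with these spending functions and 90% power, 78% of the maximum looks high. If it is wrong, anyone budgeting or scheduling from it is working with the wrong number.

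A related gap is that the paragraph calls two numbers a maximum: 438, the size the calculation requires, and 800, the number the plan intends to allow. The looks are quarters of the maximum planned enrolment, with no figure attached. The only operating characteristics reported belong to the 438 design.

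**Working it through.** **Inputs from the plan.** Grades 1, 2a, 2b, 3, 4: direct 0.50, 0.30, 0.15, 0.04, 0.01; video 0.65, 0.25, 0.07, 0.02, 0.01. Allocation 1:1, power 90%, level 0.05, Wilcoxon-Mann-Whitney test, looks at 25, 50, 75 and 100%, gamma -4 and -1.

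**Assumptions.** The base case is one-sided 0.025 (two-sided 0.05) with non-binding futility. One-sided 0.05 and binding futility were also tried.

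**1. Fixed size (stated 384).**
- Video better: 0.65×0.50 + 0.25×0.20 + 0.07×0.05 + 0.02×0.01 = 0.3787.
- Ties: 0.3250 + 0.0750 + 0.0105 + 0.0008 + 0.0001 = 0.4114.
- Probability of a better view, counting half the ties: 0.3787 + 0.2057 = 0.5844.
- Tie-corrected formula: N = (1.960 + 1.2816)² × (1 − Σp̄³) / [3 × (0.5844 − 0.5)²], where p̄ is the mean proportion in each grade. With Σp̄³ = 0.2123, N = 10.51 × 0.7877 / 0.02137 ≈ 387.
- A version with separate null and alternative variances gives 382. The stated 384 reproduces.

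**2. Group-sequential maximum (stated 438).** Recursive integration gives:
- efficacy z: 3.155, 2.818, 2.439, 2.014
- futility z: -0.409, 0.527, 1.300, 2.014
- inflation 1.130, so 384 × 1.130 = 434 and 387 × 1.130 = 437

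One-sided 0.05 gives 384 × 1.140 = 438. Binding futility gives only 418 to 421. The stated 438 reproduces, and it fits non-binding futility.

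**3. Expected size at the planned effect (stated 342).** Expected fraction = 0.25 × P(stop at look 1) + 0.50 × P(stop at look 2) + 0.75 × P(stop at look 3) + 1 × P(reach the final look).

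Worked example, one-sided 0.05, non-binding. Efficacy stops at looks 1 to 3 are 0.0830, 0.2806, 0.3473. Futility stops are 0.0165, 0.0212, 0.0273. Totals are 0.0995, 0.3018, 0.3746, leaving 0.2241 for the final look. Then 0.0249 + 0.1509 + 0.2810 + 0.2241 = 0.681, and 0.681 × 438 = 298.

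| Setting, maximum 438 | Fraction | Expected N |
|---|---|---|
| One-sided 0.025, non-binding | 0.683 | 299 |
| One-sided 0.025, binding | 0.693 | 304 |
| One-sided 0.05, non-binding | 0.681 | 298 |
| One-sided 0.05, binding | 0.691 | 303 |
| Futility crossings never stop the trial | 0.710–0.722 | 311–316 |
| Efficacy-only design | 0.739 | 324 |
| Plan | 0.78 | 342 |

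Simulation of the tied rank test with the plan's own proportions gives about 300 (100,000 runs), or 312 to 313 without futility stopping, so the gap is not an artefact of the normal approximation.

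**4. Can any effect size give 342?** With futility stopping, the expected fraction peaks at about 0.755 to 0.763 over all effects (331 to 334 patients), so 78% is never reached. Without futility stopping (one-sided 0.025), 342 is reached at about 0.87 of the planned effect, where power is about 84.5%. That contradicts the condition the sentence sets.

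**5. Possible source.** 298.5 / 384 = 0.777, so 78% matches the expected size as a share of the fixed 384. The documents do not say this; it is only an inference.

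**6. If 800 sets the looks.** Looks fall at 200, 400, 600 and 800. The same z boundaries are kept, which means futility bounds calibrated to 90% power at the maximum. At the planned effect, power is about 99%. Expected size is about 427 with one-sided 0.025 (430 if futility crossings are ignored) and 436 to 437 with one-sided 0.05, so roughly 427 to 440 allowing for the unstated settings.

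**7. Pilots.** The Patients section implies 800 − 50 = 750 to 800 − 25 = 775 analysable patients. The Pilot patients paragraph, with four listed centres, gives 4×5 = 20 to 4×10 = 40 pilots, hence 760 to 780. At 750 to 780 (one-sided 0.025), expected size is about 414 to 422 and power is still about 99%.

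**The case against.** The strongest reply is that expected size is descriptive. It sets no boundary, look, level or cap, and the figures that do the work (384 and 438) reproduce. For the 438 design the error is cautious, and 342 is far below the 800 allowed. The companion statement about crossing at looks 2 or 3 has reasonable support (0.286 + 0.354 = 0.64 in the base case). All of this stands and limits the severity. It does not rescue 342, which no setting tried at the planned effect delivers.

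Three stronger readings are tempting, and the documents do not support them:

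- **That 342 understates enrolment for an 800 maximum.** The plan ties 342 to 438 by its own arithmetic, before 800 is introduced, and never offers it as the expectation for 800.
- **That the look schedule is undetermined.** The looks refer to planned enrolment, and the number the plan says it will enrol up to is 800; 438 is what the calculation requires. The plain reading is quarters of 800. What is missing is the explicit number and whether unanalysed pilots count.
- **That the trial is underpowered or its error rate compromised.** Nothing here shows that. Leaving out power for 800 is a reporting gap, and at the planned effect that power is very high.

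The objection that 299 should not be called the single correct value is also fair. Sidedness, binding status and simulation settings are not stated, so the range belongs beside it.

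**Conclusion.** The stated 78% and N=342 are wrong for the design described. The plan's inputs give about 298 to 304 (68 to 69% of 438), so 342 is too high by 38 to 44 patients. If futility crossings never stop the trial, the range is 311 to 316 and the excess is 26 to 31.

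This rests on four equally spaced looks, the stated gamma parameters, and the planned effect scaled so that 384 patients give 90% power. It holds across both sidedness readings and both futility readings.

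Severity is minor: a planning and reporting error. The 384, the 438, the efficacy boundaries and the 5% level stand, provided one look schedule is fixed in advance. The figures for 800 are less firm, because they also depend on the effect to which the futility bounds are calibrated, which the plan does not state.

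**What to change.** - Replace 78% and N=342 with the recalculated value, about 299 (68% of 438). Declare the settings: sidedness, binding or non-binding futility, and whether a futility crossing is assumed to stop the trial.
- State the number that sets the looks and list the look sizes: 200, 400, 600 and 800 on the plain reading, less any unanalysed pilots. Fix that one schedule before the first look.
- Report power and expected size for that maximum, and the effect to which the futility bounds are calibrated. For 800, that is about 99% and roughly 427 to 440 at the planned effect, slightly fewer once pilots are removed.
- Make the pilot counts in the Patients section (25 to 50) and the Pilot patients paragraph (20 to 40 for four centres) agree, and say whether the quarters exclude pilots.

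The cost is one re-run of the design calculation and a few reworded sentences. No patients are added, and the 800 cap and efficacy boundaries stay as they are.

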#### **Funding:**

This study is an investigator-initiated study.

